1.0 Objectives

1.1 Study Objectives

Describe the purpose, specific aims or objectives. State the hypotheses to be tested.

The purpose of the proposed study is to assess the effectiveness of the addition of a single-session child sexual abuse (CSA) prevention module (*Smart Parents – Safe and Healthy Kids*) on improving parents' knowledge, attitudes, and behaviors regarding CSA prevention for parents already receiving parent-education services (e.g., The Incredible Years, Parents as Teachers, SafeCare). We hypothesize that parents who receive the parenting curriculum and the CSA prevention module will (a) demonstrate significant improvement in CSA-related knowledge, attitudes, and protective behaviors from pre-test to post-test, and (b) demonstrate higher scores on CSA-related knowledge, attitudes, and protective behaviors as compared to parents who only receive the parenting curriculum.

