2.0 Background

2.1 Scientific Background and Gaps

Describe the scientific background and gaps in current knowledge.

Child sexual abuse (CSA) is a public health problem in the United States (USDHHS, 2015) and its biopsychosocial consequences are well-documented (e.g., Noll et al., 2007, 2009, 2011). Whereas evidence-based prevention efforts for physical abuse and neglect have achieved the gold standard of reducing rates of those forms of maltreatment (e.g., SafeCare; Self-Brown et al., 2012), CSA primary prevention efforts have not (Letourneau et al., 2014). While adequate school, community, and clinical treatment CSA primary prevention programs exist, evidence-based CSA prevention programs designed for direct delivery to parents do not. Parents are the chief agents of change for children and involving parents in prevention efforts significantly enhances efficacy and uptake (Mendelson & Letourneau, 2015). Targeting high-risk parents for selective prevention is especially important because at-risk parents (i.e., parents involved with child welfare) are likely to (1) experience parenting challenges such as skills (e.g., monitoring) deficits, high stress, little social support, and (2) have their own abuse

histories (Whitaker et al., 2008). This kind of environment places children at greater risk for experiencing sexual abuse, not necessarily by parents themselves, but by other adults or older children. At-risk parents are likely to create environments where children are vulnerable to perpetrators of sexual abuse (Noll, 2008).

In Pennsylvania, many of these at-risk parents are already receiving parent-education services (e.g., The Incredible Years, Parents as Teachers, SafeCare) which teach parents the fundamentals of children’s healthy physical and emotional development, parent-child communication and relationship-building, as well as strategies to ensure children’s physical safety. However, how to create protective environments from perpetrators of sexual abuse is not covered in any of these broader existing parent-education programs. If a brief CSA prevention module was added onto preexisting services where knowledge and skills are already being taught, then a cost-effective, efficacious, widely disseminated CSA primary prevention effort could begin to address this missing prevention piece.

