In order to determine if such a prevention effort is effective, it must undergo a randomized controlled trial (RCT) that compares the hypothesized improvement in outcome among participants who receive the program to a group of participants who do not receive the intervention module. RCTs are the most rigorous way of determining whether a cause-effect relationship exists between treatment and outcome (Sibbald & Roland, 1998). An RCT is required to demonstrate that our CSA prevention program produces change in parents’ knowledge, attitudes, and protective behaviors regarding CSA prevention. This change can be demonstrated due to the random allocation of participants to either the intervention or control group because randomization ensures that no between-group systematic differences could explain the cause-effect relationship of the intervention on the outcome. To date there have been no RCTs of a single-session CSA prevention module that has been added onto an existing parent-education program. The proposed study seeks to determine if a single-session CSA prevention module (*Smart Parents – Safe and Healthy Kids*) can improve parents’ knowledge, attitudes, and protective behaviors regarding CSA prevention by being added onto The Incredible Years, Parents as Teachers, and SafeCare.

Implementing an evidence-based intervention necessitates that it is executed the way in which the intervention was originally designed. If an intervention demonstrated a positive effect on behavior, the only way one can be sure they can replicate that positive effect is to deliver the intervention in the exact same way. This process is known as implementing with fidelity. Fidelity monitoring may be done in a variety of approaches including participant report, provider report, or direct observation. Typically, interventions use one form of fidelity monitoring, but empirical studies often cite the importance of utilizing multiple methods of monitoring (Resnicow et al., 1998). Given that we are introducing an additive intervention approach to multiple parent-education models, assessing fidelity of our added module in two different methods is a secondary outcome of interest. We are including multiple methods of fidelity monitoring to assess if one method of fidelity monitoring (e.g., provider self-report, parent report, and direct observation) is sufficient. This has implications for reducing burden/cost in future work.

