7.0 Study Design and Procedures

7.1 Study Design

Describe and explain the study design.

This research will utilize a randomized controlled trial (RCT) design. As this research includes three parenting programs, Incredible Years, PAT, and SafeCare, three RCTs will be conducted simultaneously. Randomization will occur at the site level to reduce the potential for contamination; as such, recruited parents will not be informed of the randomization process. When sites agree to participate (i.e., be randomized) they agree to implement the evidence-based parenting program plus the added module as they would typically implement the parenting program. Although the module is not evidence-based, they are agreeing to deliver as if it were standard procedure.

This section describes the design and procedures for the three RCTs: (1) *Incredible Years RCT*; (2) *Parents as Teachers RCT* and (3) *SafeCare RCT*. However, there are commonalities between the three trials:

- There will be two groups of providers— one assigned to deliver the parenting program and one assigned to deliver the parenting program plus additional SPSHK module at the end of the last session (described below), in support of the research question.
- Parents in the control group will complete assessments at four time points: pre-parenting intervention, post-parenting intervention, one-week post parenting, and one month post-intervention.
- Parents in the experimental group will complete assessments at four time points: pre-parenting intervention, post-parenting intervention, post-module, and one month post-intervention.
- For the experimental group, fidelity monitoring procedures will also occur in sessions for each enrolled provider-subjects. Parents and provider-subjects of these sessions will each complete a fidelity assessment instrument. With the parent’s permission, the provider will audio record two experimental sessions.

Different measures will be asked at specific assessment periods:

Measure Name (file name in supporting documents attachments)	Construct	Timing of Delivery (by Protocol Section description paragraph)
Alabama Parenting Questionnaire (APQ; ‘Measure_APQ.docx’)	Parenting behaviors and responding to child’s externalizing behaviors: subscales of Parental Involvement, Positive Parenting, Inconsistent Discipline Practices	7.2.1, 7.2.3, 7.2.5, 7.2.6

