Immediately following delivery of the SPSHK module, those in the experimental group will complete the APQ, Module Assessment, and a questionnaire asking about their overall satisfaction with the module ('Measures_Parent Satisfaction Survey'). Parents will complete their fidelity assessment in addition to the Parent Satisfaction Survey ('SPSHK Parent Fidelity Monitoring') as part of their post-intervention assessment packet. As the parent fills out this form, the provider will complete the self-reported fidelity assessment ('SPSHK Provider Fidelity Monitoring_V2').

The audio recordings will be reviewed by the PSU study team using the 'SPSHK Research Fidelity Monitoring v2.1' form. The form assesses which aspects of the curriculum were delivered and to what degree (incomplete v. complete) to the family. These observations will be compared with provider self-report and parent report. Two visits will be recorded and scored for fidelity.

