8.2 Sample size determination

If applicable, provide a justification of the sample size outlined in section 8.1 – to include reflections on, or calculations of, the power of the study.

Parents as Teachers and SafeCare

In a two-arm RCT, sample size is determined by power and estimated effect size. We are doing a repeated measures design (4 assessments), so this must be accounted for in the sample size calculation. Assuming a desired power of .8 and estimated effect of .45, the sample size needed to detect an effect at alpha .05 is 62 individuals per group ($N = 124$) for each trial. That is, 124 participants for Parents as Teachers and 124 participants for SafeCare.

Incredible Years

Because the additive approach of our research is novel, we are relying on prior CSA prevention and general PE program research to estimate the effect size. A meta-analysis of general PE programs, from which CSA programs were excluded, found the estimated average effect size for trials including a control group to be $d = .3$. A meta-analysis of CSA-specific prevention programs (Davis & Gidycz, 2000) reported the average effect size for a single session program to be $d = .59$. Averaging these findings, we estimate the effect size of our module to be $d = .45$. The group-based delivery of IY requires the experimental design to be a cluster RCT and, as such, clustering must be considered in sample size calculation (i.e.,

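### Hypothesis (a) is a pre-post improvement claim in the module arm with no comparator, set level with the between-arm hypothesis (b); it cannot support a claim about the module

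*Combined protocol and SAP*

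**What the plan says.** Section 1.1 gives the purpose as assessing what the added module contributes for parents already in a parenting programme. It then states two hypotheses about parents who receive both. Hypothesis (a) is that they "demonstrate significant improvement in CSA-related knowledge, attitudes, and protective behaviors from pre-test to post-test", with no comparator named. Hypothesis (b) is that they "demonstrate higher scores on CSA-related knowledge, attitudes, and protective behaviors as compared to parents who only receive the parenting curriculum". The two are joined in one sentence, and nothing marks one as primary or the other as descriptive.

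Section 2.1 gives the reason for randomising: the trial "compares the hypothesized improvement in outcome among participants who receive the program to a group of participants who do not receive the intervention module".

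Section 7.1 schedules four assessments per arm, labelled T1 to T4 in section 14.0. The module arm is assessed "pre-parenting intervention, post-parenting intervention, post-module, and one month post-intervention"; the control arm is assessed "pre-parenting intervention, post-parenting intervention, one-week post parenting, and one month post-intervention". The Module Assessment is completed at all four times in both arms. The T3 timing in the module arm is set in section 7.2.4: "Immediately following delivery of the SPSHK module, those in the experimental group will complete the APQ, Module Assessment". No section says which of T1 to T4 are the pre-test and post-test of hypothesis (a).

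Section 8.3 lists t-tests, linear regression and hierarchical regression as candidates, leaves the exact models open, and says the power is for a between-factor repeated-measures ANOVA.

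**The concern.** The only assessment labelled as pre is T1, before the parenting programme. Three later ones carry a post label. If (a) runs from T1 to T3, the module arm has by then had about 14, 5 or 6 parenting sessions (section 7.2.2), completed the same instrument three times, and received the module. A change over that window is the sum of programme, retest, time and module effects. If (a) runs from T2 to T3, most of the programme effect drops out, but retesting and time remain. On either reading, an analysis of the module arm alone cannot separate the module from the rest, which is the separation section 2.1 says randomisation is there to provide.

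The control arm completes the same instrument at matched times, so the information needed is collected but not used in (a). At stake is a route to a positive statement about the module that does not depend on the module having any effect.

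**Working it through.** **The plan's own figures.** These show which hypothesis the trial was sized for.

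- Parents as Teachers and SafeCare (section 8.2): effect 0.45, power 0.80, alpha 0.05, 4 assessments, 62 per arm. Treat this as a between-factor repeated-measures ANOVA with f = 0.45/2 = 0.225, m = 4 and correlation 0.7. The noncentrality is f² × N × m / (1 + (m − 1) × 0.7), and the noncentral F gives 62 per arm, as stated. The normal approximation gives 78 × (1 + 3 × 0.7)/4 = 60.5, so 61. The 0.7 is stated for Incredible Years only; using it here is an assumption.
- Incredible Years (Equation 1): 8.0025 × (1.960 + 0.842)² / (10 × 3 × 0.45²) = 10.34, so 11 groups per condition, as stated.

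Both are between-arm calculations. The sample size serves (b).

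**Chance that (a) is met when the module does nothing.** Assume a zero module effect and a gain g, in SD units, shared by both arms. A paired t-test in the module arm has standard error sqrt(2(1 − rho)/n). At n = 62 and rho = 0.7 this is sqrt(0.6/62) = 0.098. The two-sided 5% critical value on 61 df is about 2.00, so an observed gain of 2.00 × 0.098 = 0.20 SD is significant. The noncentrality is g/0.098: 1.02, 2.03 and 3.05 for g = 0.1, 0.2 and 0.3. Probability of significant improvement, n = 62:

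| Gain g | rho 0.5 | rho 0.7 | rho 0.8 |
|---|---|---|---|
| 0.1 | 12% | 17% | 23% |
| 0.2 | 34% | 52% | 69% |
| 0.3 | 64% | 85% | 96% |

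With g = 0 it is the nominal 2.5%.

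For Incredible Years, with 140 parents in 14 groups of 10, clustering has to be allowed for. Multiply the variance by 1 + 9 × ICC, where the ICC is that of the change scores (not given in the documents; 0.05 to 0.20 assumed), and use 13 df. At ICC 0.20 and g = 0.3 the standard error is sqrt(0.6 × 2.8/140) = 0.110 and the noncentrality 2.74. Probability of significant improvement, rho = 0.7:

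| Gain g | ICC 0.05 | ICC 0.10 | ICC 0.20 |
|---|---|---|---|
| 0.1 | 22% | 18% | 13% |
| 0.2 | 65% | 54% | 39% |
| 0.3 | 94% | 87% | 72% |

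These take all 140 as analysed. The plan raised 11 groups to 14 to cover attrition and non-participation, so 140 is an upper figure.

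**The between-arm test in the same scenarios.** In 20,000 simulated trials per scenario with 62 per arm and rho = 0.7, the difference in change was significant in about 5% of runs, and in favour of the module in about 2.4%, at every g from 0 to 0.3. With a true module effect of 0.45, its standard error is sqrt(2 × 0.6/62) = 0.139 and its power about 90%. Adjusting the post-module score for baseline gives sqrt(2 × 0.51/62) = 0.128 and about 94%. Site clustering is ignored in these figures.

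**The case against.** The strongest reply is that the controlled test is already there. Hypothesis (b) is the randomised comparison, section 2.1 rests the causal claim on it, and the power calculation is for a between-arm analysis. The word joining (a) and (b) can be read as requiring both. On that reading a null module could not be declared effective more often than (b) falsely favours it, about 2.4% above. This stands, and it limits the point: the fault is the equal standing of (a), not a missing controlled test.

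A reader might infer more than the documents support in three ways.

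- That (a) is declared confirmatory and will be reported as evidence for a useless module. The protocol does not call it confirmatory, and how it would be reported is a prediction.
- That (a) is defined from T1 to T3. The window is undefined; T1 is the natural start, but T2 to T3 is not excluded.
- That 85%, or over 99% at 140 parents, is the expected false-support rate. The gain of 0.3 behind it comes from the meta-analysis that "found the estimated average effect size for trials including a control group to be" 0.3. That is a controlled effect of general parenting programmes with sexual-abuse programmes excluded, not a gain on this instrument. Section 2.1 says protection from perpetrators of sexual abuse "is not covered in any of these broader existing parent-education programs". The figure above 99% also ignores clustering.

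Against that, the host programmes do teach communication, monitoring and safety (sections 2.1 and 2.3), and a retest gain needs no relevant content. Even a gain of 0.1 SD moves the rate from 2.5% to 17% at 62 parents.

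**Conclusion.** The point holds as one of standing and definition. Hypothesis (a), tested within the module arm, cannot support a claim about the module, whichever window is meant, and giving it the same rank as (b) runs against the rationale in section 2.1. With no module effect it would be met 17% to 85% of the time at 62 parents for assumed non-module gains of 0.1 to 0.3 SD at correlation 0.7. At a gain of 0.3 the range is 64% to 96% for correlations 0.5 to 0.8. At 140 parents and a gain of 0.3 it is 72% to 94% for an assumed ICC of 0.20 to 0.05. The documents give no size for a non-module gain on this instrument, and their statement about programme content makes the lower values more plausible. The documents do not support the conclusion that the trial as a whole lacks a valid test of the module.

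**What to change.** In sections 1.1 and 8.3, state that the between-arm contrast on the Module Assessment at a named post-module time is the sole confirmatory test of the module in each trial. One suitable form is the T3 score adjusted for the T1 score, with site or group clustering allowed for. Report within-arm change in both arms descriptively, with its window named and no significance claim.

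The between-arm difference in T2 to T3 change can be supportive, since that interval contains the module. It need not be the main contrast: T3 comes straight after the session, which leaves little time for protective behaviours to change, and T2 follows a parenting programme delivered by providers already trained in the module, whereas T1 precedes any session.

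All the data are already scheduled in both arms, and this point calls for no change in sample size. The only cost is giving up (a) as a separate claim.

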1.2 Primary Study Endpoints

State the primary endpoints to be measured in the study. Clinical trials typically have a primary objective or endpoint. Additional objectives and endpoints are secondary. The endpoints (or outcomes), determined for each study subject, are the quantitative measurements required by the objectives. Measuring the selected endpoints is the goal of a trial (examples: response rate and survival).

The primary endpoint of this study is to deliver the intervention to enough parents such that we are powered to detect an effect (power calculations provided in section 8). The primary outcome on which we are detecting an effect is a project-developed measure specific to our intervention ('Measure_ParentAssessmentTool' in supporting documents). Additional outcomes of interest, but upon which the module is not contingent, include parental stress, perception of social support, mental health, substance use, readiness for change, and parenting behaviors.

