1.3 Secondary Study Endpoints

State the secondary endpoints to be measured in the study.

The secondary endpoint to be measured in the study is the degree to which the CSA module (*Smart Parents – Safe and Healthy Kids*) is implemented with fidelity. We are assessing this in three ways: parent report, provider self-report, and observation through audio recording.

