Alcohol Use Disorders Identification Test (AUDIT; ‘Measure_AUDIT.docx’)	Assesses alcohol consumption, drinking behaviors, and alcohol-related problems.	7.2.1
Center for Epidemiologic Studies Depression Scale (CES-D; ‘Measure_CESD.docx’)	Screening test for depressive symptoms and depressive disorder	7.2.1

Drug Abuse Screening Test (DAST; 'Measure_DAST.docx')	Assesses drug use, not including alcohol or tobacco use, in the past 12 months	7.2.1
Demographics ('Measure_Demographics.docx')		7.2.1
Interpersonal Support Evaluation List (ISEL; 'Measure_ISEL-SF.docx')	Perceptions of social support (Appraisal, Belonging, Tangible)	7.2.1
Parent Satisfaction Survey ('Measure_ParentSatisfactionSurvey.docx')	Satisfaction with added module	7.2.5
Module Assessment ('Measure_ParentAssessmentTool.docx')	Assessment of attitudes, knowledge, behavior of CSA prevention	7.2.1, 7.2.3, 7.2.5, 7.2.6
Readiness, Efficacy, Attributions, Defensiveness, and Importance Scale (READI-SF; 'Measure_READI-SF.docx')	Assessment of parent's readiness to engage in services	7.2.1
SPSHK Parent Fidelity Monitoring (experimental group only; 'SPSHK Parent Fidelity Monitoring_v3.docx')	Parent assessment of session fidelity	7.2.4
SPSHK Provider Fidelity Monitoring measure (provider-subjects only, of experimental sessions)	Provider self-report assessment of fidelity	7.2.4
SPSHK Researcher Fidelity Monitoring (of audio recorded session; 'SPSHK Researcher Fidelity Monitoring_v2.docx')	Researcher assessment of session fidelity	7.2.4

Time points and measures used

Assessment Time Point	(Protocol Section)	Measures
Pre-parenting Intervention Assessment	(7.2.1)	APQ AUDIT CES-D DAST Demographics ISEL-SF Module Assessment READI-SF
Post-parenting Intervention Assessment	(7.2.3)	APQ Module Assessment
One-week post parenting (control group) or Post-parenting and SPSHK Module Assessment (experimental group)	(7.2.4)	APQ Module Assessment Parent Satisfaction Survey SPSHK Parent Fidelity Monitoring (experimental group only) SPSHK Researcher Fidelity Monitoring (experimental group only) SPSHK Provider Fidelity Monitoring (experimental group only)
One-month Follow-up Assessment	(7.2.5)	APQ Module Assessment

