7.2.1 Pre-parenting Intervention Assessment

Provide a description as defined above and format accordingly.

As described above, parents are recruited to participation in the research after independently signing up to participate in Incredible Years, Parents as Teachers, or SafeCare, and the agency/site providing their parenting program would have already agreed to randomization (and experimental condition providers received their training in the SPSHK module). Following consent and before any intervention has occurred, the parents will be given a paper copy of the assessment. A member of the research team will distribute surveys (identified only by a unique code—see Section 9) at the beginning of the first session to parents who have consented to participate.

The assessment is given in a booklet format. At this assessment point, parent survey booklets include the APQ, AUDIT, CES-D, DAST, ISEL-SF, READI-SF, a demographics questionnaire, and the module assessment of parents’ attitudes, knowledge, and behaviors of CSA prevention (measures described above in Section 7.1). Providers in the group sessions (Incredible Years) will engage with parents who do not wish to participate separately at this time.

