7.2.3 Post-parenting Intervention Assessment

Provide a description as defined above and format accordingly.

Completion of the parenting intervention is specific to each parenting program. For PAT, completion of intervention (for the purposes of our research) is at the end of the fifth foundational visit. For Incredible Years, completion of intervention (for the purposes of our research) is the penultimate session – this is the last session in which content is delivered; the final session is a celebration and graduation. For SafeCare, completion of intervention (for the purposes of our research) is at the conclusion of the parenting module (6 weeks).

Parents will be provided with another paper survey. Those who have not agreed to participate in the research will be allowed to leave. Participants will complete the APQ and Module Assessment (‘Measure_ParentAssessmentTool’ in supporting documents).

7.2.4 One-week Post-parenting (control) OR Post-parenting and Module Assessment (Experimental group)

Provide a description as defined above and format accordingly.

One-week after completing the parenting program (7.2.3), parents in the control condition that have agreed to participate in the research will be contacted by the research team to complete the third assessment, the APQ, Module Assessment ('Measure_ParentAssessmentTool'). {This will happen within a normally scheduled session of PAT or SafeCare, and will require an additional visit for the IY participants}

The week after the conclusion of event 7.2.3, providers in the experimental condition deliver the Smart Parents – Safe and Healthy Kids module to their parents. The parent and provider will complete a short survey about the content of the session. This is done each time the module is delivered to measure fidelity. Additionally, provider-participants will record any two SPSHK sessions where the participating parent(s) agree to the recording. If the parent in the individual session—or any parent in the group session—declines to be audio recorded, the SPSHK module will be delivered as usual (including the fidelity survey), but the session will not be audio recorded.

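### Section 1.2 lists six additional outcomes but only one is measured after baseline, and 8.3 does not commit the main between-arm comparison to a baseline-adjusted model

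*Combined protocol and SAP*

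**What the plan says.** Section 1.2 makes the project-developed Module Assessment the primary outcome. It adds further outcomes of interest, said not to be ones the module depends on, which "include parental stress, perception of social support, mental health, substance use, readiness for change, and parenting behaviors". The between-arm hypothesis in 1.1 concerns CSA-related scores only: intervention parents should "demonstrate higher scores on CSA-related knowledge, attitudes, and protective behaviors as compared to parents who only receive the parenting curriculum". Section 1.3 makes implementation fidelity the secondary endpoint: "The secondary endpoint to be measured in the study is the degree to which the CSA module" is delivered as designed.

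Section 7.1 sets four assessments (T1 to T4 in section 14.0): "Parents in the experimental group will complete assessments at four time points: pre-parenting intervention, post-parenting intervention, post-module, and one month post-intervention". The pre-parenting row of its time-point table reads "APQ AUDIT CES-D DAST Demographics ISEL-SF Module Assessment READI-SF", and 7.2.1 agrees: "At this assessment point, parent survey booklets include the APQ, AUDIT, CES-D, DAST, ISEL-SF, READI-SF, a demographics questionnaire", plus the Module Assessment. At T2, "Participants will complete the APQ and Module Assessment". Sections 7.2.4 and 7.2.5 keep those two instruments at T3 and T4, with satisfaction and fidelity forms added at T3. On when the module is given, 7.2.4 states: "The week after the conclusion of event 7.2.3, providers in the experimental condition deliver the Smart Parents" module. T1 and T2 therefore both precede it.

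For Parents as Teachers (PAT) and SafeCare, 8.2 gives 62 per arm for power .8, effect .45 and alpha .05 in a repeated-measures design with four assessments. Section 8.3 keeps t-tests, linear regression and hierarchical regression all open, makes control for nesting conditional on recruitment, and says the trial is powered for a repeated-measures ANOVA with a between-group factor.

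**The concern.** A construct measured once, before any program content, cannot show a module effect. If 1.2 is taken at its word, readers will expect results on six additional outcomes, and the data can supply one. Later silence on the other five could be mistaken for selective reporting.

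The second issue bears on the primary outcome. The T1 Module Assessment is collected from every consenting parent, yet 8.3 does not say that the between-arm comparison will adjust for it. The options left open differ greatly in power. One reading of the ANOVA in 8.3 averages two pre-module assessments into the outcome and so dilutes any effect. With the choice unfixed, it could also be made after outcome data are seen.

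**Working it through.** **1. The six constructs against the schedule (7.1 tables, 7.2.1 to 7.2.5).**

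| Construct in 1.2 | Listed instrument | Collected at |
|---|---|---|
| Parenting behaviors | APQ | T1, T2, T3, T4 |
| Social support | ISEL-SF | T1 only |
| Mental health | CES-D | T1 only |
| Substance use | AUDIT, DAST | T1 only |
| Readiness for change | READI-SF | T1 only |
| Parental stress | none listed | – |

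Count: 1 + 4 + 1 = 6. The four baseline-only constructs rest on five scales. The CES-D row describes depressive symptoms, and the APQ subscales are involvement, positive parenting and inconsistent discipline, so neither is listed as a stress measure. The two tables in 7.1 number the later assessments differently (one refers to a 7.2.6 that does not exist), but both tie the five scales to 7.2.1.

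**2. Inputs for the power illustration.** From 8.2: n = 62 per arm, effect .45, two-sided alpha .05. From 7.2.4: the module comes after T2, so the effect is placed at T3 and T4 only. Assumed: outcome SD 1, and equal correlation r between assessments of .3, .5 or .7. The documents give no correlation for PAT or SafeCare; .7 appears in 8.2 for Incredible Years only. Clustering and attrition are ignored. For all tests but group-by-time, power comes from the noncentral t with 122 df and noncentrality δ√(62/2), where δ is the effect divided by the square root of the variance shown.

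**3. The plan's own 62.** Take a group main effect over four assessments, with .45 present at all four. The variance of the four-assessment mean is (1+3r)/4 = .475, .625, .775, and 80% power needs 37.8, 49.4 or 61.05 per arm. At r = .7 this rounds up to 62. The stated size is thus consistent with an effect present at T1 and T2 as well, but 8.2 does not state the test or the correlation, so this is inference.

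**4. Power at 62 per arm, effect at T3 and T4 only.**

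| Analysis | Variance | r=.3 | r=.5 | r=.7 |
|---|---|---|---|---|
| Post-score t-test | 1 | .70 | .70 | .70 |
| T1-to-T3 change-score t-test | 2(1−r) = 1.4, 1.0, .6 | .56 | .70 | .89 |
| T3 adjusted for T1 | 1−r² = .91, .75, .51 | .74 | .82 | .94 |
| Mean of T3 and T4 adjusted for T1 | (1+r)/2 − r² = .56, .50, .36 | .91 | .94 | .99 |
| Group-by-time, 3 df | see below | .70 | .85 | .98 |
| Group main effect, four assessments | (1+3r)/4 = .475, .625, .775 | .44 | .35 | .29 |

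For the main effect, the averaged difference is (0+0+.45+.45)/4 = .225. For group-by-time, the F noncentrality is 31 × Σ(effect − .225)²/(1−r) = 31 × .2025/(1−r) = 8.97, 12.56, 20.93, with 3 and 366 df.

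**5. Clustering.** Assume 10 parents per site and an intraclass correlation of .02 or .05 (the documents give neither for PAT or SafeCare). The design effect is 1 + 9 × ICC = 1.18 or 1.45. Dividing δ by its square root takes the T1-adjusted T3 figures from .74/.82/.94 to .67/.75/.89 or .58/.66/.82.

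**The case against.** On 1.2, the best defence is that these were always background variables. The section says the module does not depend on them, no hypothesis uses them, 1.3 names fidelity as the secondary endpoint, and the DAST asks about the past 12 months, which suits a baseline descriptor. That is plausible and makes the error minor. The text still calls them outcomes, and 8.3 gives them no role as covariates or moderators. A stress item could also sit inside an attached form; the Demographics row states no construct. The point is therefore limited to the listed instruments.

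On 8.3, a reader might infer three stronger things, and the documents support none of them.

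- That the baseline Module Assessment has no use. It does: hypothesis (a) in 1.1 is a pre-test to post-test change, and 8.2 counts T1 among the repeated measures.
- That the t-tests in 8.3 must be on post scores. The section does not say so. A change-score or paired test would use T1, although the change-score test has no more power than the post-score test at r = .3 and .5.
- That repeated-measures analysis is inferior in general. Only the four-assessment main effect fares badly. The group-by-time test exceeds the T1-adjusted T3 comparison at r = .5 and .7, and at r = .7 it is practically level with the adjusted mean of T3 and T4.

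It is also fair to say that baseline adjustment alone is incomplete: 7.1 randomizes sites, so any replacement wording must deal with clustering.

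**Conclusion.** Both parts stand at limited size. In 1.2, five of the six additional outcomes cannot yield a module effect: four for want of any post-baseline measurement, one for want of a listed instrument. It would be wrong to conclude that the trial cannot answer its main question, because the primary outcome is scheduled at all four assessments.

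In 8.3, the gap is a missing commitment to a baseline-adjusted between-arm comparison. Under the stated assumptions, adjusting the mean of T3 and T4 for T1 gives the highest power of the six analyses at every correlation tried, and the four-assessment main effect the lowest. The absolute figures depend on the assumed equal correlation and on an effect of .45 at both T3 and T4. They are illustrations for PAT and SafeCare, not predictions, and site clustering lowers them. Whether the ANOVA in 8.3 means the main effect cannot be settled from the text, which is itself a reason to specify it.

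**What to change.** In 1.2, keep parenting behaviors (APQ) as the only additional outcome. Relabel social support, mental health, substance use and readiness as baseline characteristics. Delete parental stress, or name its instrument and time points.

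In 8.3, specify the primary between-arm analysis as post-module Module Assessment scores (T3 and T4) adjusted for the T1 score, with T1 as a covariate and not as one of the averaged outcomes. State that the model accounts for site clustering and, for Incredible Years, for parenting group as well. If any of the five baseline scales will be covariates, name them before outcome data are seen.

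The cost is a wording change in 1.2 and one or two sentences in 8.3. Unless the sponsor chooses to add a stress measure, no new data, visit or survey item is needed.
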